## 1. Glossary

Term	Definition
1M, 3M, 4M, 6M, 12M	1-month, etc. used with follow-up visit windows
2 wk, 6 wk, 8 wk, 10 wk	2-week, etc. used with follow-up visit windows
ABPM	ambulatory blood pressure monitoring
ADE	adverse device effect
AE	adverse event
AH	antihypertensive
BP	blood pressure
CEC	clinical events committee
CIN	contrast-induced nephropathy
CIP	clinical investigation plan
CKD	chronic kidney disease
CRF	case report form
CTA	clinical trial agreement
DC	discharge
DD	device deficiency
DUS	duplex ultrasound
eGFR	estimated glomerular filtration rate
EC	ethics committee
EDC	electronic data capture
ESRD	end-stage renal disease
FDA	Food and Drug Administration
FMD	fibromuscular dysplasia
GCP	good clinical practice
IC	informed consent
IFU	instructions for use
IRB	institutional review board
ITT	intention-to-treat

Term	Definition
MRA	magnetic resonance angiography
OBP	office blood pressure
RDC	remote data capture
RDN	renal denervation
RF	radiofrequency
RX	rapid exchange
SADE	serious adverse device effect
SAE	serious adverse event
SBP	systolic blood pressure
SIV	site initiation visit
SNS	sympathetic nervous system
SV1, SV2	Screening Visit 1, Screening Visit 2
UADE	unanticipated adverse device effect

## 2. Synopsis

Title	Global Clinical Study of Renal Denervation in the distal main and first order branch renal arteries using the Symplicity Spyral™ multi-electrode renal denervation system (SPYRAL DYSTAL)
Clinical Study Type	Multi-center, international, prospective, interventional, single arm study
Product Name	The Symplicity Spyral™ multi-electrode renal denervation catheter (Symplicity Spyral™ catheter) and the Symplicity G3™ renal denervation RF generator (Symplicity G3™ generator)
EUDAMED number	CIV-19-12-031165
Sponsor	
Global sponsor: Medtronic Vascular, Inc. [name] United States
 
Regional sponsor: Medtronic Bakken Research Center (BRC) B.V. [name], The Netherlands
 
Note: this clinical study is funded by the Global sponsor.

Objective	The objective of this single arm interventional study is to determine if renal denervation performed in the distal main and first order branch renal arteries is as effective in reducing blood pressure as the procedural approach used in the SPYRAL HTN-OFF MED clinical study.
Product Status	Investigational in the United States. Commercially approved in countries that accept CE-mark. (Device will be used in accordance with the Instructions for Use .)
Endpoints	
Efficacy endpoints
 
The efficacy endpoints will be compared to the SPYRAL HTN-OFF MED efficacy endpoints using a propensity score stratified analysis at 3 months. At 6 months and 12 months, the endpoints will be analyzed within the SPYRAL DYSTAL study only.
 

• Change in systolic blood pressure (SBP) from baseline (Screening Visit 2) to 3, 6 and 12 months post-procedure as measured by 24-hour ambulatory blood pressure monitoring (ABPM).

	

• Change in office SBP from baseline (Screening Visit 2) to 3, 6, and 12 months post-procedure.

• Change in diastolic blood pressure (DBP) from baseline (Screening Visit 2) to 3, 6, and 12 months post-procedure as measured by 24-hour ABPM.

• Change in office DBP from baseline (Screening Visit 2) to 3, 6, and 12 months post-procedure.

• Incidence of achieving target office SBP (SBP<140 mmHg) at 3, 6, and 12 months post-procedure.

• Comparison of the pattern of BP reduction over 24 hours of ABPM between this study and the SPYRAL HTN-OFF MED study.

 
Safety endpoints
 

• Safety composite at 1, 3, 6 and 12-months post-procedure: Incidence of the following events:

- All-cause mortality

- End-stage renal disease (ESRD)

- Significant embolic event resulting in end-organ damage

- Renal artery perforation requiring intervention

- Renal artery dissection requiring intervention

- Vascular complications

- Hospitalization for hypertensive crisis not related to confirmed non-adherence with medications or the protocol

- New renal artery stenosis >70%, confirmed by angiography and as determined by the angiographic core lab at 6 months follow up

• Myocardial infarction

• Stroke

• Renal artery re-intervention

• Major bleeding according to TIMI definition (i.e., intracranial hemorrhage, <math>\geq 5</math> g/dl decrease in hemoglobin concentration, a <math>\geq 15\%</math> absolute decrease in hematocrit, or death due to bleeding within seven days of the procedure)

• Increase in serum creatinine >50% from Screening Visit 2

 
The following additional analyses will be conducted:
 

• Procedural characteristics

Study Design	Multi-center, international, prospective, interventional, single arm study treating approximately 50 subjects who will undergo the renal denervation procedure.

Study Population	Subjects with uncontrolled hypertension will be enrolled in accordance with the inclusion and exclusion criteria specified in the protocol. Approximately 350 subjects will be enrolled in order to treat approximately 50 subjects at up to 15 study centers.
Study Duration	Total study duration will be approximately 2.5 years, including enrollment up to minimally 12 months follow up (subjects will be consented for a maximum follow up of 5 years in case there are reasons that would require the follow up to be extended beyond the currently planned 12 months follow up).
Inclusion Criteria	

1. Individual is <math>\geq 20</math> and <math>\leq 80</math> years old at time of enrollment (consent).

2. Individual has an office systolic blood pressure (SBP) <math>\geq 150</math> mmHg and <math>< 180</math> mmHg and an office diastolic blood pressure (DBP) <math>\geq 90</math> mmHg measured at Screening Visit 2, according to the guidelines in Appendix 16.5.

3. Individual has a valid 24-hour ABPM average SBP <math>\geq 140</math> mmHg and <math>< 170</math> mmHg measured at Screening Visit 2, according to guidelines in Appendix 16.5. ABPM is considered valid if the number of successful daytime readings captured is <math>\geq 21</math> and the number of successful nighttime readings captured <math>\geq 12</math>.

4. Individual agrees to have all study procedures performed, and is competent and willing to provide written, informed consent to participate in this clinical study.

5. Individual is willing to discontinue current antihypertensive medications at Screening Visit 1 through the 3-month post-procedure visit.

Exclusion Criteria	

1. Individual has one or more of the following conditions: stable or unstable angina within three months of enrollment, myocardial infarction within three months of enrollment; heart failure, cerebrovascular accident or transient ischemic attack, or atrial fibrillation at any time. Subjects are permitted to take aspirin or clopidogrel for cardiovascular risk reduction. Subjects who received catheter or surgical treatment for atrial fibrillation and are in sinus rhythm are not excluded.

2. Individual has undergone prior renal denervation.

3. Individual has at least one main renal artery with a diameter of less than 3 mm or greater than 8 mm.

	

4. Individual has presence of FMD (defined as visible beading of the artery on angiography).

5. Individual has >50% stenosis in any treatable vessel.

6. Individual has a renal artery stent placed <3 months prior to the denervation procedure.

7. Individual has presence of a renal artery aneurysm defined as any localized increase in the diameter of the vessel.

8. Individual has disease not allowing any treatment in the main renal artery.

9. Individual has an estimated glomerular filtration rate (eGFR) of <45 mL/min/1.73m^2, using the 4-variable MDRD calculation (in mL/min per 1.73 m^2 = 175 x SerumCr-1.154 x age-0.203 x 1.212 (if subject is black) x 0.742 (if female)).

10. Individual has documented type 1 diabetes mellitus or poorly-controlled type 2 diabetes mellitus with glycosylated hemoglobin greater than 8.0%. (If the glycosylated hemoglobin in the subject's records is >3 months old (from the date of Screening Visit 2), or history of uncontrolled blood sugars raises concern, it is required to analyze glycosylated hemoglobin as part of Screening Visit 2 labs).

11. Individual is taking SGLT2 inhibitor or GLP-1 agonists that have been prescribed <90 days prior to Screening Visit 1 or does not plan on remaining on these drugs for the duration of the trial.

12. Individual has had  1 episode(s) of orthostatic hypotension not related to medication changes within the past year or has had a reduction of SBP ≥20 mmHg or DBP ≥10 mmHg within three minutes of standing coupled with symptoms during the screening process (at SV2).

13. Individual requires chronic oxygen support or mechanical ventilation other than nocturnal respiratory support for sleep apnea (e.g., CPAP, BiPAP).

14. Individual with a history of narcotic drug abuse, is currently on methadone, or who has used narcotic drugs more than once in the month prior to Screening Visit 1.

15. Individual had documented primary pulmonary hypertension.

--	---

	

16. Individual has untreated secondary cause of hypertension (either known or suspected) or is taking drugs that increase sympathetic tone that could contribute to hypertension.

17. Individual has frequent intermittent or chronic pain that results in treatment with non-steroidal anti-inflammatory drugs (NSAIDs) for two or more days per week over the month prior to Screening Visit 2.

18. Individual with HIV on anti-retroviral drug therapy without documentation that hypertension preceded initiation of anti-retroviral drug treatment.

19. Individual has a scheduled or planned surgery that, in the opinion of the Investigator, may affect study endpoints.

20. Individual has a documented condition that would prohibit or interfere with ability to obtain an accurate blood pressure measurement using the protocol-specified automatic/office blood pressure monitor (e.g., upper arm circumference outside cuff size ranges available by geography or arrhythmia such as atrial fibrillation that interferes with automatic monitor's pulse sensing and prohibits an accurate measurement).

21. Individual works night shifts.

22. Individual has severe cardiac valve stenosis for which, in the opinion of the investigator, a significant reduction of blood pressure is contraindicated.

23. Individual has a documented confounding medical condition, which in the opinion of the investigator, may adversely affect the safety of the participant (e.g., has clinically significant peripheral vascular disease, aortic aneurysm, bleeding disorders such as thrombocytopenia, hemophilia, or significant anemia).

24. Individual is pregnant, nursing or planning to become pregnant during the course of the study follow up. (Note: Pre-menopausal female participants must have a negative serum or urine human chorionic gonadotropin (hCG) pregnancy test prior to angiography).

25. Individual has a known unresolved history of drug use or alcohol dependency, lacks the ability to comprehend or follow instructions, or would be unlikely or unable, in the opinion of the investigator, to comply with study follow-up requirements.

--	--

	
26. Individual is currently enrolled in a concurrent investigational drug or device study, unless approved by the study sponsor. (Note: For the purpose of this protocol, participants involved in extended follow-up studies for products that were investigational but are currently commercially available are not considered enrolled in an investigational study).
 
27. Individual is currently taking anti-mineralocorticoid drugs. (Note: Subjects may be enrolled as long as anti-mineralocorticoid drugs are weaned off at least 8 weeks prior to Screening Visit 1).
 
28. Individual has an active peptic ulcer or gastrointestinal (GI) bleeding within the prior six months from consent.
 
29. Individual has a history of bleeding diathesis or coagulopathy or will refuse blood transfusions.
 
30. Individual has polycystic kidney disease, unilateral kidney, atrophic kidney, or history of renal transplant.

Follow up	Subjects will be followed up for a minimum of 12 months post-procedure (Subjects will be consented for a maximum of 5 years follow up).

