## 8.4. Exclusion Criteria

1. Individual has one or more of the following conditions: stable or unstable angina within 3 months of enrollment, myocardial infarction within 3 months of enrollment; heart failure, cerebrovascular accident or transient ischemic attack, or atrial fibrillation at any time. Patients are permitted to take aspirin or clopidogrel for cardiovascular risk reduction. Patients who received catheter or surgical treatment for atrial fibrillation and are in sinus rhythm are not excluded.
2. Individual has undergone prior renal denervation.
3. Individual has one or more main renal artery with a diameter of less than 3mm or greater than 8 mm.
4. Individual has the presence of FMD (defined as visible beading of the artery on angiography).
5. Individual has >50% stenosis in any treatable vessel.
6. Individual has a renal artery stent placed <3 months prior to the denervation procedure.
7. Individual has presence of a renal artery aneurysm defined as any localized increase in the diameter of the vessel.
8. Individual has disease not allowing any treatment in the main renal artery.
9. Individual has an estimated glomerular filtration rate (eGFR) of <45 mL/min/1.73m^2, using the 4 variable MDRD calculation (in mL/min per 1.73 m^2 = 175 x SerumCr-1.154 x age-0.203 x 1.212 (if patient is black) x 0.742 (if female)).
10. Individual has documented type 1 diabetes mellitus or poorly-controlled type 2 diabetes mellitus with glycosylated hemoglobin greater than 8.0%. (If the glycosylated hemoglobin in the patient's records is >3 months old (from the date of Screening Visit 2), or history of uncontrolled blood sugars raises concern, it is required to analyze glycosylated hemoglobin as part of Screening Visit 2 labs.)
11. Individual is taking SGLT2 inhibitor or GLP-1 agonists that have been prescribed <90 days prior to SV1 or who does not plan on remaining on these drugs for the duration of the trial.
12. Individual has had  $\geq 1$  episode(s) of orthostatic hypotension not related to medication changes within the past year or has a reduction of SBP  $\geq 20$  mmHg or DBP  $\geq 10$  mmHg within 3 minutes of standing coupled with symptoms during the screening process (at SV2).
13. Individual requires chronic oxygen support or mechanical ventilation other than nocturnal respiratory support for sleep apnea (e.g. CPAP, BiPAP).

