#### 13.2.3. *Per Protocol Population*

All treated subjects, meeting the following criteria are included in the per protocol population analysis::

1. Subjects showing medication compliance in blood and/or urine (via drug testing data) at Screening Visit 2 (SV2) and three months post-procedure.
2. Exclude subjects with protocol deviation code 101 (consent not obtained).

3. Exclude subjects who do not meet the following inclusion/exclusion criteria:

- Inclusion: Individual has an office systolic blood pressure (SBP)  $\geq 150$  mmHg and  $< 180$  mmHg and an office DBP  $\geq 90$  mmHg measured at Screening Visit 2, according to the guidelines in **Appendix 16.5** of the CIP.
- Inclusion: Individual has a 24-hour ABPM average SBP  $\geq 140$  and  $< 170$  mmHg measured at Screening Visit 2, according to guidelines in **Appendix 16.5** of the study protocol.
- Exclusion: Individual has undergone prior renal denervation.
- Exclusion: Individual has renal artery anatomy that is ineligible for treatment.
- Exclusion: Individual has one or more of the following conditions: stable or unstable angina within three months of enrollment, myocardial infarction within three months of enrollment; heart failure, cerebrovascular accident or transient ischemic attack, or atrial fibrillation at any time.

4. Exclude subjects meeting the anti-hypertensive medication escape criteria (OSBP  $> 180$  mmHg or safety reasons).

Office and ambulatory blood pressure outcomes out to three months will be presented for this population.

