7.1.3.3. Per Protocol Population

All treated subjects, meeting the following criteria:

1. Subjects showing medication compliance in blood and/or urine (via drug testing data) at screening visit 2 (SV2) and 3-months.
2. Exclude subjects with protocol deviation code 101 (consent not obtained).
3. Exclude subjects who do not meet the following Inclusion/Exclusion criteria.
 - Inclusion: Individual has an office systolic blood pressure (SBP) \geq 150 mmHg and $<$ 180 mmHg and an office DBP \geq 90 mmHg measured at SV2, according to the guidelines in Appendix 16.5 of the study protocol.
 - Inclusion: Individual has a 24-hour ABPM average SBP \geq 140 and $<$ 170 mmHg measured at SV2, according to guidelines in Appendix 16.5 of the study protocol.
 - Exclusion: Individual has undergone prior renal denervation.
 - Exclusion: Individual has renal artery anatomy that is ineligible for treatment.
 - Exclusion: Individual has one or more of the following conditions: stable or unstable angina within 3 months of enrollment, myocardial infarction within 3 months of enrollment; heart failure; cerebrovascular accident or transient ischemic attack or atrial fibrillation at any time.
4. Exclude Subjects meeting the anti hypertensive medication escape criteria (OSBP \geq 180 mmHg or safety reasons).
5. Exclude subjects who did not receive the treatment.

Office and ambulatory blood pressure outcomes up to 3 months will be presented for this population.

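### The per-protocol set restates Exclusion Criterion 1 without its exception for treated atrial fibrillation, so read literally it drops eligible subjects from a secondary analysis

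*Protocol*

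**What the plan says.** Exclusion Criterion 1 appears in the protocol synopsis and again in section 8.4. Both versions list the excluded cardiovascular conditions, including atrial fibrillation at any time, and then qualify the list. The synopsis says "Subjects who received catheter or surgical treatment for atrial fibrillation and are in sinus rhythm are not excluded". Section 8.4 says "Patients who received catheter or surgical treatment for atrial fibrillation and are in sinus rhythm are not excluded".

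The per-protocol population is defined in protocol section 13.2.3 and SAP section 7.1.3.3. It starts from treated subjects and removes those who fail a selected list of eligibility criteria. The cardiovascular bullet in the protocol ends "heart failure, cerebrovascular accident or transient ischemic attack, or atrial fibrillation at any time". In the SAP it ends "heart failure; cerebrovascular accident or transient ischemic attack or atrial fibrillation at any time". The exception follows in neither document, and neither bullet refers to section 8.4.

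The same list contains an anatomy bullet: "Exclusion: Individual has renal artery anatomy that is ineligible for treatment". Exclusion criteria 3 to 8 give the specific renal-artery rules, for example "Individual has at least one main renal artery with a diameter of less than 3 mm or greater than 8 mm" (criterion 3) and "Individual has disease not allowing any treatment in the main renal artery" (criterion 8).

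Protocol section 13.4 and SAP section 7.7.2.1 make the intention-to-treat population primary and the per-protocol population secondary for the three-month comparison with the HTN-OFF MED denervation arm.

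**The concern.** A per-protocol rule that checks eligibility should remove subjects who breached a criterion and keep those who met it. Here the restated criterion is stricter than the criterion itself. A subject with ablated atrial fibrillation who is in sinus rhythm may be enrolled and treated without any deviation, and is then removed by the analysis rule for a history that the entry rule allows.

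The SAP is the document from which the analysis is programmed. Its section 8 has two programmers produce and validate the output independently. Both could follow the text exactly and agree, because the fault would lie in the specification and not in the code. If the discrepancy were noticed only once outcomes were available, someone would have to decide then who belongs in the set.

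**Working it through.** **Text comparison, Exclusion Criterion 1**

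| Element | Synopsis and section 8.4 | Protocol 13.2.3 and SAP 7.1.3.3 |
|---|---|---|
| Angina or myocardial infarction within three months | excluded | excluded |
| Heart failure, stroke or transient ischemic attack, atrial fibrillation, at any time | excluded | excluded |
| Aspirin or clopidogrel use | permitted | not mentioned |
| Treated atrial fibrillation, now in sinus rhythm | not excluded | not mentioned, so caught by the row on atrial fibrillation |

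Two sentences were lost, and they differ in effect. Leaving out the aspirin and clopidogrel sentence changes nothing, because no remaining words exclude users of those drugs. Leaving out the atrial fibrillation sentence reverses the result for one group, because the remaining words do exclude them.

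**Subjects affected**

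The plan states no figure on this point, so there is none to reproduce. Inputs:
- n = 50 treated subjects (synopsis, Study Design).
- q = proportion of treated subjects with treated atrial fibrillation in sinus rhythm. The documents do not give it; 0.5% to 5% is assumed.

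Expected number wrongly removed = n × q. Chance of at least one = 1 − (1 − q)^n.

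| q | Expected | Chance of at least one |
|---|---|---|
| 0.5% | 50 × 0.005 = 0.25 | 1 − 0.995^50 = 22% |
| 1% | 50 × 0.01 = 0.5 | 1 − 0.99^50 = 39% |
| 2% | 50 × 0.02 = 1.0 | 1 − 0.98^50 = 64% |
| 5% | 50 × 0.05 = 2.5 | 1 − 0.95^50 = 92% |

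**Effect on precision**

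Protocol section 13.3 gives, for 38 HTN-OFF MED subjects, a mean change in ambulatory systolic pressure of −5.5 mmHg with 95% CI −9.1 to −2.0 and p = 0.003.

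- Half-width of that interval = (9.1 − 2.0)/2 = 3.55 mmHg.
- SE = 3.55 / t(0.975, 37 df) = 1.75 mmHg.
- SD = 1.75 × √38 = 10.8 mmHg.
- Check: t = −5.5/1.75 = −3.14, p = 0.0033, which agrees with the stated p-value.

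With this SD, the 95% half-width for a single-group mean is t(0.975, n − 1) × 10.8/√n. It is 3.07 mmHg at n = 50, 3.10 at n = 49 and 3.17 at n = 47. Wrongly removing one to three subjects therefore widens the interval by 0.03 to 0.10 mmHg. This is a benchmark only: the real per-protocol set will already be smaller than 50 after the drug-test and escape exclusions, and the planned estimate is a stratified difference between studies.

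No matching count is given for the comparator. Protocol section 3.1 reports 166 subjects randomized to denervation, but SAP Table 1 adds a secondary cohort whose size is not stated. The documents also do not say how the per-protocol rule is applied to HTN-OFF MED subjects.

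**The case against.** The strongest defense is that the per-protocol bullets are abbreviations. The lead-in asks whether a subject failed an inclusion or exclusion criterion, and a subject with treated atrial fibrillation in sinus rhythm has not. Other text is shortened too, such as the aspirin and clopidogrel sentence and the ABPM validity rule. On this view wrongful removal is a possible programming error and not a certain result.

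Part of this stands: a programmer who went back to section 8.4 would reach the right answer. But nothing in the bullet points there. The blood-pressure bullets beside it do cite Appendix 16.5, which contains the ABPM validity rule, so that omission is covered. The atrial fibrillation omission is not.

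A second defense is that the consequence is small. That stands in full. The set is secondary, the study has no powered hypothesis, and nothing in the documents suggests that subjects with treated atrial fibrillation respond differently to denervation. No systematic shift in the estimated effect can therefore be claimed.

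A reader might go further on anatomy and infer that the per-protocol set uses a criterion DYSTAL does not have, and that it therefore keeps ineligible subjects. The documents do not support this. The anatomy bullet is not one of the numbered exclusions, but it stands under the same lead-in about failing eligibility and reads naturally as an umbrella for criteria 3 to 8. Protocol section 9.1.5.1 itself speaks of confirming eligible anatomy by angiography in every subject. Section 9.4 lists treatment of a subject who did not meet the criteria as an example of a deviation, so being treated does not imply being eligible. Only if the bullet were narrowed to mean technically untreatable would a subject in breach of criteria 3 to 7 stay in, and the text does not require that reading.

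**Conclusion.** The point holds for atrial fibrillation. In both documents the stated per-protocol rule contradicts Exclusion Criterion 1 for one expressly admitted group, and applied as written it removes eligible, correctly treated subjects.

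The size is modest and rests on an assumed prevalence: 0.25 to 2.5 of about 50 subjects at 0.5% to 5%, with a 22% to 92% chance that at least one is affected. The demonstrable cost is a slight loss of precision and a set that does not match its own eligibility rule. The intention-to-treat primary analysis is untouched.

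On anatomy, what remains is a missing cross-reference. It is worth closing because protocol section 5.2.2 and SAP section 5 say that the anatomical criteria differ between the two studies, and neither document says which set governs the HTN-OFF MED subjects in the per-protocol comparison. This is a low-priority correction.

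**What to change.** In protocol section 13.2.3 and SAP section 7.1.3.3, replace the cardiovascular bullet with a reference to Exclusion Criterion 1 as written in section 8.4, stating that the exception for treated atrial fibrillation in sinus rhythm is included. State that the same wording applies to HTN-OFF MED subjects in the per-protocol comparison.

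As a clarification, have the anatomy bullet refer to exclusion criteria 3 to 8 of section 8.4, and add a sentence saying which anatomical criteria apply to the HTN-OFF MED subjects.

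The cost is a wording change in two places. Protocol section 14.1 already has inclusion and exclusion criteria checked against source for all treated subjects, so no extra subjects, visits or procedures are needed for DYSTAL. Whether treated atrial fibrillation can be identified in the HTN-OFF MED data should be confirmed before the rule is applied there.
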